11.3.3. Analysis of the Secondary Endpoints

The analysis of the secondary endpoints will be performed at the time of the first interim analysis in a similar manner as for the dual-primary endpoints.

11.4. Pharmacokinetic Analyses

Population PK analysis of plasma concentration-time data of apalutamide will be performed using nonlinear mixed-effects modeling. The population PK modeling will include all subjects with sufficient and interpretable PK assessments. The data from the population PK samples may be combined together with the data from other studies for the population PK analysis. If sufficient data are available, the relationship of exposure to apalutamide and JNJ-56142060 to measures of efficacy and AEs may also be analyzed. The population PK/PD analysis results will be presented in a separate report. For details on the analysis of the samples from the leuprolide sub-study, see [Attachment 5](#).

11.5. Biomarker Analyses

Initial biomarker analyses will be conducted on plasma and whole blood samples to assess the frequency of AR^{F876L} mutation and other resistance markers respectively from both treatment groups. Sample size is estimated based on previously reported data and is sufficient to estimate the frequency of AR mutation and AR-V7 splice variants (95% CI) and to provide 80% power to detect associations with treatment response at a significance level of 0.05.^{1,18}

Further associations may be made with clinical endpoints with:

- F876L mutation in plasma DNA collected at EOT
- AR splice variants or other RNA anomalies in whole blood
- Other DNA anomalies in plasma samples
- AR signaling strength in archival tumor samples and blood samples collected at baseline

Immunohistochemistry on FFPE samples may be performed to identify patients with high, medium and low expression of immune markers and their association with treatment response using appropriate categorical or regression methods.

The association of the rest of the biomarkers with clinical response or relevant survival endpoints may be assessed using appropriate statistical methods (eg, analysis of variance [ANOVA], categorical or survival models), depending on the endpoints. Analyses may be performed within

and between each treatment group. Other clinical covariates (such as baseline tumor characteristics and patient demographics) may also be included in the model. Correlation of baseline biomarker expression levels with clinical response or relevant time-to-event endpoints may be performed to identify responsive (or resistant) subgroups. Association of biomarkers with clinical response or relevant time-to-event endpoints will also be explored in the overall population. Appropriate details of these exploratory analyses will be included in the Statistical Analysis Plan. Results of these exploratory analyses will be presented in separate technical reports.

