Kaplan-Meier product limit method and Cox proportional hazards model will be used to estimate the time-to-event variables and to obtain the HR along with the associated confidence intervals.

Interim Analysis

For the dual-primary OS endpoint, 2 interim analyses are planned for this study after observing approximately 50% (~205 events) and approximately 70% (~287 events) of the total number of required (410) events. At the time of the first interim analysis of OS, the final analysis of the rPFS dual-primary endpoint will also be performed. No interim analysis is planned for the rPFS endpoint.

Population PK and PD Analysis

Population PK analysis of plasma concentration-time data of apalutamide will be performed using nonlinear mixed-effects modeling. If sufficient data are available, the relationship of exposure to apalutamide and JNJ-56142060 to measures of efficacy and AEs may also be analyzed. The population PK/PD analysis results will be presented in a separate report.

Leuprolide PK Analysis

Descriptive statistics of leuprolide PK data will be summarized by treatment groups (with apalutamide or placebo) and dose of leuprolide acetate. Statistical analysis to compare leuprolide concentrations when administered alone or in combination with apalutamide will be performed. The percentage of subjects with testosterone levels <50 ng/dL will be summarized descriptively by treatment groups.

Biomarker Analysis

The associations of the biomarkers with clinical response or time-to-event endpoints may be assessed using appropriate statistical methods (such as analysis of variance [ANOVA], categorical, or survival models), depending on the endpoint. A detailed Statistical Analysis Plan will be prepared for these exploratory studies and the results will be reported in a separate report.

Medical Resource Utilization Analysis

The analysis of this data will be included in a separate report.

Safety Analysis

The safety parameters to be evaluated are the incidence and intensity of treatment-emergent AEs, clinically significant changes in the subject's physical examination findings, vital signs measurements, and clinical laboratory results. Exposure to study drug and reasons for discontinuation of study treatment will be tabulated.

TIME AND EVENTS SCHEDULE (SCREENING, TREATMENT, AND FOLLOW-UP PHASES)

		Screening Phase	Treatment Phase			Follow-up Phase

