2. OBJECTIVES AND HYPOTHESIS

2.1. Objectives

Primary Objective

The primary objective is to determine if the addition of apalutamide to ADT provides superior efficacy in improving radiographic progression-free survival (rPFS) or OS for subjects with mHSPC.

Secondary Objectives

- To evaluate clinically relevant improvements with addition of apalutamide to ADT including delays in pain progression and opioid use for prostate cancer, skeletal-related events (SREs), and the need for cytotoxic chemotherapy
- To characterize the safety of adding apalutamide to ADT in subjects with mHSPC
- To characterize the population pharmacokinetics (PK) and pharmacodynamics (PD) of apalutamide
- To evaluate the concentration of leuprolide and assess the PD effect of leuprolide on testosterone concentrations when used alone or in combination with apalutamide
- To evaluate the treatment effectiveness with the addition of apalutamide to ADT for the subpopulations of subjects with low-volume or high-volume mHSPC

Other Objectives

- To evaluate exploratory biomarkers predictive of response and resistance to treatment
- To evaluate patient relevant outcomes including symptoms (ie, pain, fatigue, urination) and function (ie, physical, emotional, social) and health-related quality of life
- To evaluate improvements in other clinically relevant endpoints with the addition of apalutamide to ADT
- To collect medical resource utilization (MRU) data that may be used in future economic modeling (the construction and reporting of the economic model will be conducted separately from this study)

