## **8. BIOMARKERS**

Exploratory biomarker analysis of AR anomalies and other markers previously shown to be responsible for resistance to apalutamide will be conducted and will be reported in a separate document. To determine the appropriate biomarker threshold, statistical method for evaluating treatment effect on biomarker subgroup may be utilized as appropriate.

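### For baseline biomarkers, neither analysis route described tests whether the apalutamide effect depends on the marker, which is what a predictive marker means

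*Protocol*

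**What the plan says.** Among the other objectives (Protocol 2.1) is this one: "To evaluate exploratory biomarkers predictive of response and resistance to treatment". Protocol 11.5 gives one route for baseline markers, with its purpose: "Correlation of baseline biomarker expression levels with clinical response or relevant time-to-event endpoints may be performed to identify responsive (or resistant) subgroups". It continues: "Association of biomarkers with clinical response or relevant time-to-event endpoints will also be explored in the overall population". SAP section 8 gives a second route: "To determine the appropriate biomarker threshold, statistical method for evaluating treatment effect on biomarker subgroup may be utilized as appropriate".

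Four other statements bear on the point:

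- Protocol 11.5 allows analyses within "and between each treatment group. Other clinical covariates (such as baseline tumor characteristics and patient demographics) may also be included in the model". It names no model term or test for comparing arms.
- Protocol 11.5 calls the sample size sufficient "to provide 80% power to detect associations with treatment response at a significance level of 0.05". The current text gives no number of subjects, marker prevalence or effect size behind that figure.
- The Protocol synopsis (Biomarker Analysis) promises more: "A detailed Statistical Analysis Plan will be prepared for these exploratory studies and the results will be reported in a separate report". That plan is not among the documents, and SAP section 8 is only two sentences long.
- The main SAP's method for clinical subgroups (5.2.1.3) is a Cox hazard ratio within each subgroup. A treatment-by-marker interaction test is not named in either document.

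**The concern.** A marker is predictive if the apalutamide effect differs by marker level. The matching null hypothesis is that the treatment hazard ratio is the same whatever the marker value. The two routes address other questions:

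- Correlating baseline marker level with outcome tests whether the marker is prognostic. A marker of aggressive disease would separate outcomes just as well in men who never took the drug.
- Evaluating the treatment effect in a marker subgroup tests whether apalutamide works in those men. If it works in everyone, as the sample size assumes, the test tends to be significant for any marker, including one unrelated to the disease.

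At stake is the label. A prognostic marker could be reported as defining a resistant subgroup, or a threshold could be set for a marker that says nothing about who benefits. Protocol 9.4 chooses tissue markers partly because they represent high-risk disease and says that the information could guide therapies, so prognostic markers are likely to be among those examined. The randomized placebo arm is what allows prognosis and prediction to be separated, and neither route is described as using it for that purpose.

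**Working it through.** **Inputs from the documents.** Protocol 11.2 gives 1:1 allocation, an exponential rPFS distribution, a control median of 20 months, a hazard ratio (HR) of 0.67, 368 rPFS events, two-sided alpha 0.005, at least 85% power, about 1,000 subjects and 30 months of enrollment.

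**Assumptions.** The number of men with biomarker samples is taken as 220, 500 or 1,000. The amendment log mentions 220 and 500 and says that the 220 limit was later passed; 1,000 is the whole trial. Marker prevalence is 50%. A prognostic marker has HR 1.5 and a noise marker HR 1.0. The treatment HR is 0.67 at every marker level, so no marker is predictive. Tests are two-sided at 5%.

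**The plan's own figure.** Events = 4(z₀.₉₉₇₅ + z₀.₈₅)² / (ln 0.67)² = 4(2.807 + 1.036)² / 0.1604 ≈ 369, against 368 stated. The treatment effect used below is therefore the plan's own. The 80% biomarker power cannot be reproduced, because its inputs are not given.

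**Events by sample size.** Scaling 368 events per 1,000 men gives 81 at 220, 184 at 500 and 368 at 1,000.

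**Route 1, prognostic marker, arms pooled.** The approximate rejection rate is Φ(√(D/4) × ln 1.5 − 1.96), with ln 1.5 = 0.405:

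- D = 81: Φ(1.82 − 1.96) ≈ 45%
- D = 184: Φ(2.75 − 1.96) ≈ 79%
- D = 368: Φ(3.89 − 1.96) ≈ 97%

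**Route 2, noise marker, treatment effect in the marker-high half.** With D/2 events, the rate is Φ(√(D/8) × 0.4005 − 1.96), where 0.4005 = |ln 0.67|:

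- D = 81: Φ(1.27 − 1.96) ≈ 25%
- D = 184: Φ(1.92 − 1.96) ≈ 48%
- D = 368: Φ(2.72 − 1.96) ≈ 78%

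**Simulation of the same settings.** Rates are rounded. The overall control median is about 20 months, accrual is uniform over 30 months, and the cut at about 32 months gives close to 368 events at n = 1,000.

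| Test at nominal 5%, no predictive marker | n = 220 | n = 500 | n = 1,000 |
|---|---|---|---|
| Prognostic marker vs outcome, arms pooled | 43% | 77% | 97% |
| Prognostic marker vs outcome, placebo arm alone | 26% | 55% | 84% |
| Noise marker, treatment effect in the marker-high half | 25% | 49% | 76% |
| Treatment-by-marker interaction | about 5% | about 5% | about 5% |

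The placebo row is the clearest. Men who never received apalutamide would yield an apparent resistant subgroup in a quarter to more than four-fifths of trials.

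**Boundary cases.** With a noise marker, Route 1 rejects in about 5% of trials. With no drug effect, Route 2 rejects in about 5%.

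**Power of the interaction test.** With four equal cells, the variance of the log ratio of HRs is about 16/D, so power = Φ(√(D/16) × |ln r| − 1.96). At D = 368, √(368/16) = 4.80:

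- r = 0.67: Φ(4.80 × 0.4005 − 1.96) ≈ 48%
- r = 0.50: Φ(4.80 × 0.693 − 1.96) ≈ 91%

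At 81 and 184 events, power is 14% and 27% for r = 0.67, and 34% and 65% for r = 0.50. For 80% power, 16(1.960 + 0.842)² / (ln r)² gives about 784 events for r = 0.67 and 262 for r = 0.50.

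**The case against.** The strongest reply is that the test may already be specified elsewhere. A separate biomarker plan is promised, and analyses between treatment groups are allowed, which could include comparing marker associations across arms; that comparison is the interaction. This stands as far as it goes: the documents do not show that the final biomarker analysis will be wrong. It does not remove the point, because 11.5 and SAP section 8 state methods together with purposes, and those purposes need a test that neither section names.

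Several stronger readings are tempting but not supported:

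- *That predictive markers will be identified by these two routes.* Both are worded as options, and no decision or labelling rule is given.
- *That both routes reject for any irrelevant marker.* Route 1 is inflated only if the marker is prognostic. That is plausible for disease markers, but the HR of 1.5 is an assumption.
- *That the Route 2 rejections are false positives.* With HR 0.67 in everyone, a treatment effect in the marker-high half is real. It misleads only if read as showing that the marker predicts benefit.
- *That a size can be put on a threshold search.* SAP section 8 cites a paper on a biomarker threshold design but does not describe the procedure, so no figure for it is justified here.
- *That all the biomarker work is affected.* Much of it concerns acquired resistance, with samples at Cycle 12 and end of treatment. A baseline interaction does not apply to markers measured after treatment has started.

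**Conclusion.** For baseline markers the point holds. The two routes described test prognosis and subgroup efficacy, while the objective is prediction, and no test of whether the treatment effect varies by marker is named. Under the stated assumptions, a marker that predicts nothing about the drug would look notable in about 43% to 97% of trials if it is prognostic and analyzed with arms pooled. If it is noise and judged by the treatment effect in its high half, the range is about 25% to 76%. The interaction test stays at about 5%. The sizes depend on the assumed sample size, prevalence and prognostic HR; the mismatch of hypotheses does not.

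Priority is low. This is an exploratory objective reported separately, with no role in the rPFS, OS or secondary claims. Exploratory status excuses low power and multiplicity, but not a label that the test cannot support.

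**What to change.** In Protocol 11.5, SAP section 8 and the biomarker analysis plan:

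1. Call a baseline marker predictive, responsive or resistant, or set a threshold for it, only on the basis of a treatment-by-marker interaction. Use a Cox model fitted to both arms, with the main effects and the randomization strata included, and report the interaction estimate with its confidence interval.
2. Report marker-outcome associations, pooled or within an arm, as prognostic.
3. Keep resistance markers measured at Cycle 12 or end of treatment descriptive and outside this rule.
4. State that the 80% power in 11.5 refers to associations and does not carry over to the interaction.

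The samples and data stay the same, so the direct cost is wording. The real cost is power: at 368 events, about 48% for a ratio of HRs of 0.67 and 91% for 0.50, and less if fewer men gave samples. Fewer markers will be called predictive, and the biomarker report should say so.

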11.6. Medical Resource Utilization

The analysis will be prepared separately and will not be a part of the clinical study report.

11.7. Safety Analyses

The safety parameters to be evaluated are the incidence, intensity, and type of AEs, vital signs (blood pressure), ECG, and clinical laboratory results. Exposure to study drug and reasons for discontinuation of study treatment will be tabulated.

Adverse Events

The verbatim terms used in the eCRF by investigators to identify AEs will be coded using the most current Medical Dictionary for Regulatory Activities (MedDRA) and will be graded according to NCI-CTCAE (Version 4.03). Treatment-emergent AEs are AEs that occur or worsen on or after first dose of study drug through 30 days after the last dose of study drug and will be included in the analysis. Adverse events will be summarized by system organ class and preferred term, and will be presented overall and by treatment group. Serious adverse events and deaths will be provided in a listing. All AEs resulting in discontinuation, dose modification, dosing interruption, or treatment delay of study drug will also be listed and tabulated by preferred term.

Clinical Laboratory Tests

Clinical laboratory test results will be collected from Screening and through 30 days after last dose of study drug. Laboratory data will be summarized by type of laboratory test. Parameters with predefined NCI-CTCAE (Version 4.03) toxicity grades will be summarized. Change from baseline to the worst AE grade experienced by the subject during the study will be provided as shift tables.

Electrocardiogram (ECG)

Electrocardiogram data obtained at screening will be summarized by ECG parameter.

Vital Signs

Descriptive statistics of blood pressure (systolic and diastolic) values and changes from baseline will be summarized at each scheduled time point. The percentage of subjects with values beyond clinically important limits will be summarized.

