9.1.4. End-of-Treatment Visit

An EOT Visit will be scheduled within 30 days after the last dose of study drug for all subjects, except those lost to follow-up, the subject died, or the subject withdrew consent to study participation. Subjects who discontinued from treatment due to progression, AE, or other reasons should have the EOT Visit completed before starting any subsequent therapy for prostate cancer.

If a subject is unable to return to the site for the EOT Visit, the subject should be contacted to collect AEs that occur within 30 days after the last dose of study drug.

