10.2. Discontinuation of Study Drug

If a subject's study drug must be discontinued before disease progression this will not result in automatic withdrawal of the subject from the study. If the subject has radiographic progression

without clinical progression and alternate therapy is not initiated, treatment may continue until clinical progression is observed. All attempts should be made to capture radiographic progression even in subjects who have evidence of clinical progression.

However, a subject's study treatment must be discontinued for:

- Clinical progression defined as:
 - Deterioration in ECOG PS grade to grade 3 or higher (related to prostate cancer progression)
 - Need to initiate any of the following because of tumor progression (even in the absence of radiographic evidence of disease)
 - Subsequent anti-cancer therapy for metastatic prostate cancer
 - Radiation therapy for metastatic prostate cancer lesion(s) (palliative radiation to lesions existing at baseline will not be considered clinical progression)
 - Surgical interventions for complications due to metastatic prostate cancer progression. (Note: Surgical interventions for complications of local-regional progression are not considered clinical progression)
 - Need for chronic opioid analgesics: For subjects entering the study without receiving opioids, chronic opioid use is defined as administration of opioid analgesics lasting for ≥ 3 weeks for oral or ≥ 7 days for non-oral formulations. For subjects entering the study already receiving opioids, chronic opioid use is defined as a $\geq 30\%$ increase in total daily dose of the opioid analgesics lasting for ≥ 3 weeks for oral or ≥ 7 days for non-oral formulations. NOTE: Administration of as needed (eg, not fixed or scheduled dosage) use of opioid analgesics or extended opioid use for treatment other than the subject's prostate cancer does not require discontinuation from study treatment (eg, codeine/acetaminophen combinations, hydrocodone/acetaminophen combinations, hydrocodone/ibuprofen combinations, oxycodone/acetaminophen combinations, oxycodone/aspirin combinations, tramadol)
- More than 2 dose level reductions for Grade 3 or higher treatment-related AEs (see [Table 1](#) and [Table 2](#))
- Seizure of any grade or Grade 4 neurotoxicity
- Subjects who have had their treatment assignment unblinded for any reason except for IDMC recommendation to unblind the study

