12.3. Procedures

12.3.1. All Adverse Events

All AEs and special reporting situations, whether serious or non-serious, will be reported from the time a signed and dated ICF is obtained until 30 days after the last dose of study drug. Serious adverse events, including those spontaneously reported to the investigator within 30 days after the last dose of study drug, must be reported using the Serious Adverse Event Form. The sponsor will evaluate any safety information that is spontaneously reported by an investigator beyond the time frame specified in the protocol.

All events that meet the definition of an SAE will be reported as SAEs, regardless of whether they are protocol-specific assessments. Anticipated events will be recorded and reported as described in [Attachment 4](#). Some countries will not identify anticipated events for the Health Authorities.

All AEs, regardless of seriousness, severity, or presumed relationship to study drug, must be recorded using medical terminology in the source document and the eCRF. Whenever possible, diagnoses should be given when signs and symptoms are due to a common etiology (eg, cough, runny nose, sneezing, sore throat, and head congestion should be reported as "upper respiratory infection"). Investigators must record in the eCRF their opinion concerning the relationship of the AE to study therapy. All measures required for AE management must be recorded in the source document and reported according to sponsor instructions.

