#### **4.5. Pre-study and Concomitant Therapy**

Concomitant medications, other than study treatment, and medications taken prior to starting study treatment will be summarized for all subjects using the Safety population analysis set by treatment group. Medications are considered concomitant if taken during the treatment period (from the date of first dose through 30 days after the last dose of study drug, except subsequent therapies for prostate cancer). Medications will be summarized by World Health Organization (WHO) drug therapeutic class and generic medication name.

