## 6. SAFETY

### 6.1. Adverse Events

Subjects will be assessed for AEs at each monthly clinic visit while on the study. Adverse events will be graded according to the NCI-CTCAE Version 4.03 and coded to preferred term and system organ class (SOC) using the most recent version of MedDRA.

All AEs reported during the AE reporting period (inclusive of the 30-day post last dose of study drug period) will be considered as treatment-emergent adverse events and will be summarized by treatment group as treated using all subjects in the safety population.

For each treatment group, AE incidence rates will be summarized with frequency and percentage by SOC and preferred term, with all subjects treated in that treatment group as the denominator, unless otherwise specified. In addition, AE incidence rates will also be summarized by severity and relationship to study drug. Treatment-related AEs are those judged by the Investigator to be at least possibly related to the blinded study drug. Subjects with multiple occurrences of events will only be counted once at the maximum severity to study drug for each preferred term, SOC, and overall. Deaths that occur within 30 days after the last dose of study drug are defined as on-study deaths.

AE onset date will not be imputed if it's completely missing. Partial AE onset date will be imputed as follows:

- If the AE onset date is missing day only, it will be set to:
  - the first day of the month that the AE occurred, if the month/year of the onset of AE is different from the month/year of the study treatment start;
  - the day of the study treatment start, if the month/year of the onset of AE is the same as month/year of the study treatment start but different from the month/year of the AE resolution date;

- the day of the study treatment start or the day of AE resolution date, whichever is earlier if the month/year of the onset of AE and month/year of the study treatment start and month/year of the AE resolution date are same;
- If the AE onset date is missing both day and month, it will be set to the earliest of:
  - January 1 of the year of onset, as long as this date is after the study treatment start;
  - the day and month of the study treatment start, if this date is the same year as that the AE occurred;
  - the AE resolution date.

Summary tables of the following AEs will be provided:

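### The treatment-emergent window is not split at the start of subsequent prostate cancer therapy, so the all-cause adverse event tables can include toxicity of next-line drugs

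*Protocol*

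**What the plan says.** Protocol 11.7 defines treatment-emergent events as those that "occur or worsen on or after first dose of study drug through 30 days after the last dose of study drug". SAP 6.1 is equally broad: "All AEs reported during the AE reporting period (inclusive of the 30-day post last dose of study drug period) will be considered as treatment-emergent". Collection covers the same tail, since under Protocol 12.3.1 adverse events "will be reported from the time a signed and dated ICF is obtained until 30 days after the last dose of study drug".

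Subsequent therapy may start inside that tail. Protocol 9.1.4 states that "An EOT Visit will be scheduled within 30 days after the last dose of study drug for all subjects", and that subjects who stop treatment "should have the EOT Visit completed before starting any subsequent therapy for prostate cancer". This sets an order of events but no 30-day wait. Protocol 10.2 lists among the grounds for stopping study drug the need to initiate "Subsequent anti-cancer therapy for metastatic prostate cancer", so a prompt switch is foreseeable.

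The SAP treats next-line therapy separately in two other places. SAP 4.5 takes medications as concomitant "from the date of first dose through 30 days after the last dose of study drug, except subsequent therapies for prostate cancer". SAP Table 2 censors rPFS at the last tumor assessment before selected new systemic anticancer therapy. The adverse event section has no corresponding rule.

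**The concern.** An event caused by a drug started, say, ten days after the last dose of study drug enters the treatment-emergent tables under the randomized arm. The drug that caused it is left out of the concomitant medication summary for the same days. A reader of the Grade 3 or 4 or serious event tables cannot tell whether an event arose before or after the switch.

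The contamination need not be equal between arms. The design assumes that placebo subjects progress earlier, and time to cytotoxic chemotherapy is a secondary endpoint. SAP 6.1 reports crude incidence over all treated subjects. If more placebo subjects have switched by the data cut-off, more next-line events fall in the placebo column.

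**Working it through.** **1. The rule.** Set side by side, Protocol 11.7 and SAP 6.1 end the window only at 30 days after the last dose, and Protocol 9.1.4 permits next therapy after an End-of-Treatment Visit held at any time in those 30 days. The overlap follows from the text and needs no arithmetic.

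**2. The plan's own figure.** The only basis in the documents for a difference between arms is the pair of assumed rPFS medians, 20 and 30 months (Protocol 11.2). The event count built on them reproduces: d = 4(z₀.₉₉₇₅ + z₀.₈₅)² / (ln 0.67)² = 4(2.807 + 1.036)² / 0.1604 ≈ 369, against 368 stated. Power with 368 events is 84.9%.

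**3. Expected switchers.** Inputs from the plan: 500 subjects per arm, accrual over about 30 months, exponential rPFS. Assumptions added here: uniform accrual, no dropout, and each rPFS event ends study drug. The share with an event by month T is

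F(T) = 1 − [exp(−h(T − 30)) − exp(−hT)] / (30h), with h = ln 2/20 on control and ln 2/30 on apalutamide.

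The 368 events are reached at T ≈ 32.1 months. This is close to the month (32.2) at which 205 deaths are expected under a control median OS of 44 months and a hazard ratio of 0.75.

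| | Control | Apalutamide |
|---|---|---|
| F(32.1) | 0.423 | 0.313 |
| Subjects with an event | 211 | 157 |

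The ratio is 211/157 ≈ 1.35. By month 54 it is 365/293 ≈ 1.25.

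**4. Illustrative size.** Let q be the share of these subjects who start next therapy inside the window, and r the chance that such a subject has a new adverse event from it before day 30. The documents give neither. With q from 25% to 75% and r from 10% to 50% (assumed), the share of all subjects affected is F × q × r:

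- Control: 0.423 × 0.25 × 0.10 ≈ 1.1% to 0.423 × 0.75 × 0.50 ≈ 15.8%
- Apalutamide: 0.313 × 0.25 × 0.10 ≈ 0.8% to 0.313 × 0.75 × 0.50 ≈ 11.8%
- Difference: about 0.3 to 4.1 points more on placebo

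With both q and r between 20% and 50%, the difference is 0.4 to 2.7 points.

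**5. Person-time.** With q as above and a start on day 7 to day 21, the time after the start of next therapy is 0.25% to 1.9% of treatment-emergent person-time on control and 0.17% to 1.3% on apalutamide. The control maximum, for example, is 211.3 × 0.75 × (23/30.44) ≈ 120 person-months out of 6,097 + 211.3 × (30/30.44) ≈ 6,305.

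**6. Exposure in the same model.** Mean time on drug by month 32 is F/h: 0.423 × 20/ln 2 ≈ 12.2 months on control and 0.313 × 30/ln 2 ≈ 13.6 months on apalutamide, about 11% more. A background event seen in 10% of placebo subjects would be seen in roughly 10% × 13.6/12.2 ≈ 11% on apalutamide.

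**The case against.** The strongest reply is that the affected tables are all-cause by design and the plan already has a filter. SAP 6.1 defines treatment-related events by investigator judgement and tabulates them overall, by grade and for Grades 3 or 4, with treatment-related serious events in the overall summary. Events leading to discontinuation or dose modification of study drug cannot come from a drug started after study drug stopped. Every treatment-emergent serious event gets a narrative. This stands: a reader might infer that next-line toxicity is reported as study-drug toxicity throughout, and the documents do not support that. The filter does not, however, repair the all-cause comparison between arms.

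Second, the placebo excess is inferred. Study drug may continue after radiographic progression, rPFS events include deaths that lead to no next therapy, and stops for toxicity could act in the opposite direction. This also stands. Step 3 is nearer an upper bound than a forecast.

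Third, the percentage points in step 4 do not convert into table rates. They cover any new event over all terms, while SAP 6.1 counts a subject once per preferred term, per system organ class and overall. A subject with an earlier event adds nothing to the overall rate, the excess in any single term is a fraction of the total, and no Grade 3 or 4 figure can be derived.

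Three stronger readings are tempting: that the artefact masks harm from apalutamide, that the bias grows with efficacy, and that any between-arm difference in terms unrelated to study drug would be artefact. None is shown. Longer exposure on apalutamide pushes crude rates the other way (step 6), and chance and sequelae of progression also produce differences. The net direction for a given term is therefore open.

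Finally, cutting the main window would shorten it unequally by arm and lean on attribution to retain late events. That is a fair argument against replacing the 30-day definition, but not against adding a split.

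**Conclusion.** The gap holds. In both documents the treatment-emergent window runs past the start of subsequent therapy, while the SAP separates that therapy for concomitant medication and for rPFS. The all-cause tables for any event, Grade 3 or 4 events and serious events can therefore contain next-line toxicity.

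More of it on placebo is an expectation resting on the assumed rPFS medians and on earlier stopping in that arm; the documents do not state it. Its size cannot be determined from them. The 0.3 to 4.1 points are an illustration that depends on q and r and on treating an rPFS event as the end of study drug. The conclusion is limited to an avoidable ambiguity in the all-cause safety comparison, worth resolving before the data are tabulated. It does not show that the safety comparison is biased in apalutamide's favour overall.

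**What to change.** Leave adverse event collection to day 30 and the 30-day treatment-emergent definition as they are. In SAP 6.1, prespecify that the key all-cause tables (any treatment-emergent event, Grade 3 or 4, and serious, by system organ class, preferred term and arm) are also produced with the window ending at the earlier of 30 days after the last dose and the day before the first subsequent anticancer therapy. Keep in that version any later event judged related to study drug. Show the remaining events to day 30 in a separate table for events after the start of subsequent therapy, so that nothing is lost.

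No new data should be needed. Protocol 9.1.5 already collects the first subsequent therapy, and the rPFS censoring rule in SAP Table 2 cannot be applied without a start date for new systemic therapy. The cost is SAP wording, programming and a few extra tables. One drawback remains: a late study-drug event that the investigator judges unrelated moves to the separate table, where it is still reported.
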